4.2 Scientific Rationale for Study Design

This is primarily an implementation study to determine the feasibility of incorporating PGx testing as part of clinical care. Secondarily, we will use a historical control of GI cancer patients enrolled into PMBB to determine the safety and effectiveness of genotype-guided chemotherapy dosing. We performed qualitative interviews of 16 GI oncologists within Penn Medicine, and 6 (38%) stated that it would be unethical to randomize patients who may be carrying these variants to receive full-dose chemotherapy that could result in severe life-threatening toxicity. Five of the 10 oncologists supported study randomization, but as a clinician acknowledged the challenges in consenting a sufficient number of patients to undergo randomized PGx testing as this study design is not typically viewed favorably from the patient perspective.

4.3 Study Intervention

The study utilizes a laboratory developed test performed in a CLIA environment for determining PGx variants in *DYPD* and *UGT1A1* from genomic DNA isolated from a blood or saliva sample (see section 6.1.1 and Appendix 14.5 Validation Reports).

4.4 Dose Adjustments based on Genotype

Genotype-guided dose recommendations will be made according to peer-reviewed, evidence-based clinical guidelines from the NIH-funded Clinical Pharmacogenetics Implementation Consortium (CPIC) for 5-FU and capecitabine and the Dutch Pharmacogenetics Working Group (DPWG) for irinotecan (refer to Tables 2 and 3).^{3,12}

Table 2. Genotype-guided dosing recommendations

Drug(s)	Gene	Genotype	Gene Activity Score*	Phenotype	Clinical Implication	Dose Recommendation
5-FU, capecitabine	DYPD	See Table 3 below	2	Normal Metabolizer	Patient is predicted to have a normal risk of toxicity when treated with 5-FU or capecitabine.	Initiate 5-FU or capecitabine at the standard dose.
			1.5	Intermediate Metabolizer	Patient is predicted to have an increased risk of severe toxicity when treated with 5-FU or capecitabine.	Reduce starting dose by 50% followed by dose titration based on toxicity. 5-FU Bolus: if standard dose is 400 mg/m ² , consider 200 mg /m ² 5-FU CIV: If standard dose is 2400 mg/m ² , consider 1200 mg/m ² Capecitabine: If standard dose is 1000-1250 mg/m ² , consider 500-625 mg/m ²

		1	Intermediate Metabolizer	Patient is predicted to have an increased risk of severe toxicity when treated with 5-FU or capecitabine.	
Reduce starting dose by 50% followed by dose titration based on toxicity.
 
5-FU Bolus: if standard dose is 400 mg/m², consider 200 mg /m²
 
5-FU CIV: If standard dose is 2400 mg/m², consider 1200 mg/m²
 
Capecitabine: If standard dose is 1000-1250 mg/m², consider 500-625 mg/m²
	
		0.5	Poor Metabolizer	Patient is predicted to have an increased risk of severe toxicity when treated with 5-FU or capecitabine.	
Avoid use of 5-FU or capecitabine-based regimens. If alternative agents not considered a suitable option, 5-FU should be administered at a strongly reduced dose (i.e. <25% of normal starting dose) with early therapeutic drug monitoring.
	
		0	Poor metabolizer	Patient is predicted to have an increased risk of severe toxicity when treated with 5-FU or capecitabine.	
Avoid use of 5-FU or capecitabine-based regimens.
	
Irinotecan, Liposomal irinotecan	UGT1A1	*1/*1	N/A	Normal Metabolizer	Patient is predicted to have a normal risk of toxicity when treated with irinotecan.	Initiate irinotecan at the standard dose.
		*1/*28	N/A	Intermediate Metabolizer	Patient is predicted to have a normal risk of toxicity when treated with irinotecan.	Initiate irinotecan at the standard starting dose.
		*1/*6				
		*28/*28 *6/*6 *6/*28	N/A	Poor Metabolizer	Patient is predicted to have an increased risk of severe toxicity when treated with irinotecan.	
Irinotecan: Reduce starting dose by 30%. If tolerated, increase dose based on the neutrophil count.
 
Liposomal irinotecan: Initiate 50 mg/m² IV over 90 minutes. Increase to 70 mg/m² IV as tolerated in subsequent cycles.

Table 3. DPYD activity scoring system

DPYD Allele/rsID	*Activity Value	Allele Function
*1	1	Normal
*2A	0	None
*5	1	Normal
*6	1	Normal
*8	0	None
*9A	1	Normal
*10	0	None
*12	0	None
*13	0	None
HapB3 (rs75017182, rs56038477, rs56276561)	0.5	Decreased
rs115232898	0.5	Decreased
rs67376798	0.5	Decreased
rs2297595	1	Normal

Calculating a DPYD activity score

1. An activity score is used to interpret DPYD genetic test results and assign phenotypes.
2. Each *DPYD* variant allele is assigned a value according to its enzyme function: 1 for normal function, 0.5 for decreased function, and 0 for no function (or minimal DPD activity). The Allele Functionality table can be found at <https://cpicpgx.org/guidelines/guideline-for-fluoropyrimidines-and-dpyd> to assign values to alleles.
3. The activity score is then calculated as the sum of the two *DPYD* variants with the lowest variant activity score to correspond to a phenotype.

Example: A patient's *DPYD* PGx test results are reported as *DPYD* *1/*2A. The *1 allele has a value of 1 and *2A allele has a value of 0, so the sum of these would yield an activity score of 1. This patient would then be classified as being an intermediate metabolizer.

4.5 Plasma uracil measurements

A 5 mL venous blood sample for measurement of plasma uracil will be collected in EDTA tubes from during the baseline visit if time and resources permit. After collection the blood sample will be kept on ice (2-4 °C) and processed to plasma in a timely fashion (processing to begin within 1 hour of sample procurement) as described below under section 7.7.

4.6 Optional Microbiome Substudy

Participants consenting to the optional microbiome substudy will provide two stool samples, one at baseline and a second sample anytime during the 6-month study period. Participants will be provided with collection materials, packaging and instructions for collecting the stool at home and bringing it to usual clinic visits.

5 STUDY POPULATION AND DURATION OF PARTICIPATION

5.1 Inclusion Criteria

In order to be eligible to participate in this study, an individual must meet all of the following criteria:

1. Able and willing to provide informed consent
2. Male or female, aged 18 years or older at the time of study initiation
3. Pathologically confirmed gastrointestinal malignancy for which treatment with a fluoropyrimidine and/or irinotecan is indicated
4. Willing to undergo blood or saliva sampling for PGx testing and comply with all study-related procedures
5. Life expectancy of at least 6 months

5.2 Exclusion Criteria

An individual who meets any of the following criteria will be excluded from participation in this study:

Exclusion criteria

1. Prior treatment with irinotecan
2. *DPYD* or *UGT1A1* genotype already known
3. Severe renal or hepatic impairment (or unacceptable laboratory values), including:
 - Neutrophil count of $<1.5 \times 10^9/L$, platelet count of $<100 \times 10^9/L$
 - Hepatic function as defined by serum bilirubin $>1.5 \times$ upper limit of normal (ULN), alanine aminotransferase (ALT), and aspartate aminotransferase (AST) $>2.5 \times$ ULN, or in case of liver metastases ALT and AST $>5 \times$ ULN
 - Renal function as defined by serum creatinine $>1.5 \times$ ULN, or creatinine clearance $<60 \text{ ml/min}$ (by Cockcroft-Gault Equation)
4. Women who are pregnant or breast feeding, or subjects who refuse to use reliable contraceptive methods throughout the study
5. Treating physician does not want subject to participate

5.3 Screen Failures

Screen failures in this study will be defined as participants who meet criteria for study enrollment but decline to participate or the treating oncologist declines participation of their patient in the study. A minimal set of screen failure information is required to ensure transparent reporting of screen failure participants, to meet the Consolidated Standards of Reporting Trials (CONSORT) publishing requirements and to respond to queries from regulatory authorities. Minimal information includes demography, screen failure details, and eligibility criteria.

5.4 Participant recruitment

Approximately 1000 cases of GI cancer are treated annually at PCAM, 150 cases at PPMC, and 200 at LGH. Roughly 100 unique patients receive fluoropyrimidine and/or irinotecan-based chemotherapy regimen in a typical month at the PCAM GI cancer clinic. Based on the frequency of *DYPD* and *UGT1A1* variants and the number of GI cancer patients seen within Penn Medicine, we anticipate that testing 500-800 patients in this multisite study would result in 45-70 patients with the actionable genotypes (see Table 4). Approximately 20% of the GI cancer population at Penn Medicine is of African ancestry. All recruitment will be done through the Penn cancer centers and treating oncologists. Clinic schedules will be screened by the clinical research coordinator for new patients with GI cancer being evaluated for treatment. Prior to the scheduled visit, the research coordinator will notify the treating oncologist about potential eligible participants and remind them of the study. The treating oncologist will discuss the study with the patient during the evaluation visit and consent will be obtained by the treating GI oncology provider (physician or advanced practice provider) or the research coordinator. This will occur in person or by remote consent. Patients will be given a copy of the official informed consent form and an opportunity to ask questions. Patients will be given sufficient time to consider participating in the trial.

Participants who complete the patient questionnaire regarding attitudes towards PGx testing will receive a \$25 gift card. The Greenphire ClinCard will be used to disburse funds and mailed to the patient.

Women of childbearing potential who are pregnant or breastfeeding will not be recruited into this study due to the risk of fetal harm caused by exposure to 5-FU, capecitabine, or irinotecan and the potential for serious adverse reactions in breastfed infants. A pregnancy test is not routinely performed in these patients at Penn Medicine thus will not be included as a study procedure.

Table 4. Anticipated study initiation and estimated participant accrual across sites

Calendar year	Q1 2021	Q2 2021	Q3 2021	Q4 2021	Q1 2022	Site totals
Site						
PCAM (20/mo)	60	60	60	60		240
PPMC (10/mo)		30	30	30	30	120
LGH (20/mo)		60	60	60	60	240
Total						600

5.5 Duration of study participation

Total involvement for each participant will be 6 months.

5.6 End of Study Definition

A participant is considered to have completed the study if he or she has completed all phases of the study including the last visit or the last scheduled procedure shown in the Schedule of Activities (SoA), Appendix Section 14.1.

6 STUDY INTERVENTION

6.1 Study Intervention(s) Administration

6.1.1 *Study Intervention Description*

This study will utilize a laboratory developed test for PGx variants in *DYPD* and *UGT1A1* performed in a CLIA-approved environment. Samples will be genotyped using the Infinium Global Screening Array v2 (Illumina, San Diego, CA), a genome-wide genotyping array that contains PGx variants. Genotyping will be performed on Illumina's iScan System at CAG at CHOP. The *DYPD* SNPs of interest *2A (rs3918290), *5 (rs1801159), *6 (rs1801160), *8 (rs1801266), *9A (rs1801265), *10 (rs1801268), *12 (rs78060119), *13 (rs55886062), rs2297595, rs115232898, rs67376798, HapB3 (rs75017182, rs56038477, rs56276561) and *UGT1A1* SNPs *6 (rs4148323) and *28 (rs8175347) will be extracted from the array data.

The *UGT1A1**28 SNP contains a (TA) tandem repeat. Samples will undergo a PCR-based assay for amplification and fragment analysis. In the validation report, thirteen samples were processed with a fragment analysis assay and compared to previous results obtained using next-generation sequencing (NGS) to determine concordance with TA repeat number in the *UGT1A1* gene. All samples were concordant with the previous results, rendering the assay to be highly sensitive, specific, reproducible, and repeatable. Sanger sequencing was used to confirm the *DYPD* and *UGT1A1**6 SNPs. All results were concordant showing 100% repeatability and reproducibility.

6.1.2 *Dosing and Administration*

Dosing for 5-FU, capecitabine and irinotecan will be recommended according to the patients' *DYPD* and/or *UGT1A1* genotype as indicated in Table 2 in Section 4.4.4. Ultimate dosing decisions will be determined by the treating oncologists according to their best clinical judgment.

6.2 Study Intervention Compliance

Compliance to the PGx testing will be determined by tracking test orders in PennChart. Central laboratory records will be reviewed to determine time of the sample acquisition, time of sample receipt in the central lab, time receipt in the genotyping facility (e.g. CAG), and time of results posted within PennChart. Test turnaround time will be determined based on the time from sample acquisition to posting of results in PennChart.

6.3 Discontinuation of Study Intervention

If the patient and/or treating oncologist wish to discontinue the PGx test and the sample as already been collected, the patient sample will be discarded. Participants will not be contacted for surveys.

6.4 Participant Discontinuation/Withdrawal from the Study

Participants are free to withdraw from participation in the study at any time upon request, without prejudice to their medical care, and are not obliged to state their reasons. The study investigator may discontinue or withdraw a patient from the study at any time for the following reasons:

- Pregnancy
- Patient transfers care outside of Penn Medicine
- Treating oncologist wishes patient to withdraw

The reason for participant discontinuation or withdrawal from the study will be recorded on the patient's Case Report Form (CRF). Subjects who sign the informed consent form but do not undergo genotyping may be replaced. Subjects who sign the informed consent form and do undergo genotyping, and subsequently withdraw, or are withdrawn or discontinued from the study, will not be replaced.

6.5 Lost To Follow-Up

A participant will be considered lost to follow-up if he or she fails to return for completion of scheduled chemotherapy infusion appointments. There are no study specific visits. Data is collected at the time of usual clinic visit and from the medical record

The following actions will be taken if a participant fails to return to the clinic for a scheduled visit/follow up:

- The research coordinator will contact the treating oncologist and ensure the reason for not returning is not a (serious) adverse event ((S)AE)
- If patient wishes to discontinue in the study, an attempt will be made to establish that the true reason is not an AE (bearing in mind that the patient is not obligated to share his/her reasons).
- If treatment is prematurely discontinued, the primary reasons for discontinuation must be recorded in the patient's file and all efforts will be made to complete and report the observations as thoroughly as possible.

- A complete final evaluation following the patient's withdrawal will be made, and any AEs will be followed up until resolution or a period of 30 days from the last dose of chemotherapy has elapsed, whichever is shorter.

7 STUDY ASSESSMENT AND PROCEDURES

7.1 Informed Consent (Baseline)

Eligibility for the study test will be determined by study personnel who will screen the clinic schedule. Study personnel will inform the treating oncologist of eligible patients by email or in person on the day of the evaluation visit. Participants will be consented in-person during the same visit or via remote consent (telephone/electronic). Blood or saliva sample will be collected on the same day if possible to ensure results will be returned prior to the first dose of chemotherapy.

7.2 Genotyping (0-14 days)

Study personnel will place an order for the PGx test in PennChart to be signed by the medical oncologist. If saliva is not self-collected by the patient in clinic, the phlebotomist will obtain a blood sample that will be sent to the Center for Applied Genomics (CAG) at the Children's Hospital of Philadelphia by courier.

7.3 Implementation Metrics (0-14 days)

The following information if available will be collected to determine the feasibility of PGx test implementation and agreement to the PGx guided dosing recommendations:

- Dates of sample collection, return of PGx test within PennChart, and timing of first dose of chemotherapy
- Intended and prescribed doses of chemotherapy
- Reasons for not adhering to the PGx guided recommendations
- The proportion of tests ordered compared to the number eligible for testing.

7.4 Baseline clinical data collection

The following information will be obtained at screening and from the patient medical record if performed as part of usual care and available in the medical record:

- Signed informed consent form
- Inclusion and exclusion criteria
- Demographic data: age, gender, race/ethnicity
- Cancer history: GI tumor type, stage, previous cancer treatments, number of lines of therapy
- Routine physical examination: ECOG performance status (see Appendix 14.2), height (cm), weight (kg)
- Vital signs: heart rate, blood pressure
- Hematology: hemoglobin, hematocrit, white blood cell count, ANC, neutrophils, eosinophils, basophils, lymphocytes, monocytes, platelets

- Clinical chemistry: sodium, potassium, calcium, glucose, creatinine, BUN, AST, ALT, alkaline phosphatase, total bilirubin, albumin
- Creatinine clearance (using Cockcroft-Gault formula)
- Concomitant medications (including dose, unit, frequency, route of administration and indication)

7.5 Data collection at each chemotherapy infusion (time 0 to 6 cycles)

The following information will be assessed at each chemotherapy visit by study personnel or extracted from the medical record with each chemotherapy treatment during the first six cycles if performed as part of usual care and available in the medical record.

- Routine physical examination: height (cm), weight (kg), calculated body mass index (BMI)
- Vital signs: heart rate, blood pressure
- Hematology: hemoglobin, hematocrit, white blood cell count, ANC, neutrophils, eosinophils, basophils, lymphocytes, monocytes, platelets prior to treatment
- Clinical chemistry: sodium, potassium, calcium, glucose, creatinine, BUN, AST, ALT, alkaline phosphatase, total bilirubin, albumin
- Creatinine clearance (using Cockcroft-Gault formula)
- Concomitant medications (including start date, dose, unit, frequency, route of administration and indication)
- Chemotherapy course: dates of treatment, dose of each treatment for first 6 cycles
- Adverse events: date of reported treatment-related symptoms, date of emergency department (ED) visits and/or hospitalizations (if applicable), clinical course and symptom duration, ED/hospitalization medical billing information. Severe TRAEs are defined as those requiring treatment in the hospital, ED, or Oncology Evaluation Center (OEC).
- Serial questionnaires assessing patient reported outcomes (PROs) for symptoms associated with adverse events will be prospectively collected by the study team at the time of each treatment for the first 6 cycles (see data collection tool in Appendix 14.6)

The following information will be extracted from the medical records and/or tumor registry at the 6-month (\pm 2 months) follow-up period if performed as part of usual care and recorded in the medical record.

- Overall patient survival (duration of patient survival from time of treatment initiation)
- Progression free survival (time from treatment initiation until disease progression or worsening)
- Information regarding tumor response from computed tomography (CT) scans will also be collected as available. This is expected to be classified by the treating oncologist as complete response (CR), partial response (PR), stable disease (SD), or progressive

disease (PD) per response evaluation criteria in solid tumors (RECIST) guideline version 1.1.

7.6 Patient Survey on attitudes towards pharmacogenetic testing (0-6 months)

Patients will complete an electronic survey via an emailed/texted link in RedCap to assess their knowledge and attitudes towards pharmacogenetics (Appendix 14.7). A paper copy will be made available for those without computer access. Patients will be contacted about the survey three times, after which time the survey will be recorded as missing data.

7.7 Plasma uracil assay (PCAM only)

If the patient is willing, a plasma sample will be obtained during the baseline visit as described in 4.5 above. Samples will be marked with a coded study-specific patient de-identifier. Blood samples will be centrifuged at 1500 g for 10 minutes in a refrigerated centrifuge (2-4°C) and plasma aliquots separated. Plasma will be stored in -80°C freezers until analysis. Plasma uracil concentrations will be determined by UPLC-MS/MS (ultra-high performance liquid chromatography – dual mass spectrometry), using a previously published and validated assay with any necessary minor modifications in collaboration with the clinical pharmacology lab at the Norris Cotton Cancer Center at Dartmouth-Hitchcock.¹⁷

7.8 Optional Microbiome study (PCAM only)

If participants consent to this portion of the study, participants will be provided a stool collection kit during the baseline visit. Participants will be instructed on home stool collection methods and will be required to collect a stool sample and bring it with them to their first chemotherapy infusion visit and one other clinical visit. Study staff will provide the participant with collection materials, packaging and instructions for collecting the stool at home and bringing it to the study visits (Appendix 14.8). Participants will be provided with ice packs and container in which to store the sample. Immediately after voiding the sample, the participant will rate the stool on the Bristol Stool Chart (Appendix 14.8.1). The study coordinator will bring this stool sample to the study lab on the 11th floor Smilow Center for Translational Research (SCTR). Lab personnel will aliquot the stool sample into 4 spoon-top vials and stored at -80°C for microbiome sequencing and fecal metabolomics.

8 STATISTICAL PLAN

8.1 Sample size

For the implementation aims, the sample size is based on average GI oncology clinical volume and anticipated number of patients that are eligible for testing. We anticipated testing 500-800 patients during the course of the study at the three Penn Medicine sites. No hypothesis testing will be performed.

For the effectiveness aims, we hypothesize that the chemotherapy-related severe TRAEs will decrease from 60% in the variant carriers receiving full dose chemotherapy in the historical control group enrolled into the PMBB to 30% in variant carriers receiving genotype guided chemotherapy.¹⁸ The following table presents the power for different sample sizes per group and different expected proportions experiencing severe TRAEs in the PGx group, based on two-sided Fisher's exact test at the alpha level of 0.05 (Table 5). Based on the frequencies of *DPYD* and/or *UGT1A1* in the population (~10%), testing 500 patients in each group will result in ~50 patients with actionable genotypes.

Table 5. Power estimate for the reduction in Severe TRAEs with PGx testing

Toxicity rate	39% in PGx	35% in PGx	30% in PGx
N in each group with actionable variants			
18	17.8%	24.8%	35.6%
36	32.3%	45.8%	63.6%
48			80%
54	49.4%	66.3%	83.9%
70		80%	
72	67.4%	82.9%	
97	80%		

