	*13	c.1679T>G	I560S	rs55886062	0.001	0.000	No function
	HapB3	c.1236G>A	E412E	rs56038477	0.024	0.003	Decreased function
		c. 1129-5923C>G	-	rs75017182			Decreased function
		c.483+18G>A	-	rs56276561			Decreased function
		c.557A>G	Y186C	rs115232898	0.0001	0.012	Decreased function
		c.2846A>T	D949V	rs67376798	0.004	0.003	Decreased function
UGT1A1	*6	c.211G>A	G71R	rs4148323	0.008	0.004	Decreased function
	*28	c.-41_-40dupTA(TA ₇)	-	rs8175347	0.316	0.373	Decreased function

MAF minor allele frequency, EA European ancestry, AA African ancestry

The NIH-funded Clinical Pharmacogenetics Implementation Consortium, which issues evidence-based peer-reviewed guidelines on clinically actionable PGx variants, recommends a 50% dose reduction in individuals with one reduced function allele (intermediate metabolizers) and avoidance of therapy in those with two reduced function alleles (poor metabolizers).¹ Recent studies have shown that preemptive genotyping for *DPYD* variants can significantly reduce drug-related adverse events and improve patient safety.⁸⁻¹⁰ In a 2018 multicenter European study, Henricks et al. demonstrated the feasibility of prospective genotype-guided fluoropyrimidine dosing in clinical practice. When comparing the safety outcomes in dose-reduced variant carriers to a historical control given the standard dose, severe toxicity was found to be higher in the standard dose population (39% vs. 23%, p=0.0013).⁹ A study conducted by Kleinjan et al. in 2019 further supports the practice of *DPYD* genotype-guided dosing, demonstrating that performing initial dose reductions of capecitabine in heterozygous *DPYD* variant carriers followed by tolerance-based dose escalation did not lead to higher toxicity compared to patients of wild-type status (37.9% vs. 27.3%, p=0.54).¹⁰ There are few studies directly investigating the decreased function c.557A>G variant with evidence currently limited to case reports.⁵

The FDA drug labeling for irinotecan recommends approximately a 20-40% reduction in the starting dose in *UGT1A1* *28/*28 homozygous individuals (poor metabolizers) to avoid hematological toxicity.¹¹ The Dutch Pharmacogenetics Working Group from the Royal Dutch Pharmacists Association recommends an initial dose reduction of 30% in poor metabolizers, with subsequent dose escalation guided by patient tolerance and neutrophil counts.¹² A 2007 meta-analysis by Hoskins et al. evaluating a variety of irinotecan-containing regimens found that

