4 STUDY PLAN

4.1 Study Design

This is a non-randomized, prospective, open-label implementation study to determine the feasibility of establishing and integrating a PGx test into clinical care. The effectiveness aims will be assessed by comparing toxicity outcomes using a historical control group without clinical genotyping. The implementation will be deployed across cancer care sites within Penn medicine in sequential fashion, starting with PCAM followed by PPMC, and LGH.

Patients with a GI malignancy initiating chemotherapy with a fluoropyrimidine (5-FU or capecitabine) and/or irinotecan will be consented to undergo *DYPD* and *UGT1A1* genotyping, the study intervention. The PGx test order will be placed by the research coordinator and signed by the medical oncologist; a blood sample will be obtained by the phlebotomist, or saliva self-collected by the patient in clinic, and sent to CAG for genotyping. Results will be returned in the Precision Medicine tab in PennChart. For patients with an actionable genotype (variants that would require a dose adjustment of 5-FU, capecitabine or irinotecan), clinical decision support (CDS) tools will alert the ordering oncologist of the PGx result and the recommended dose adjustment. The prescribing oncologist will ultimately decide the chemotherapy dose incorporating clinical and genetic factors. The efficacy and safety of this PGx-guided approach will be determined by comparing the incidence of severe treatment related adverse events to a historical control group of GI cancer patients enrolled into PMBB.

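### The ~10% actionable-genotype rate in 8.1 does not follow from the protocol's own allele frequencies (about 17%) without an unstated irinotecan share, and ~50 carriers is not the size of either gene-specific comparison in the SAP

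*Combined protocol and SAP*

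**What the plan says.** Protocol 8.1 (Sample size) supports the effectiveness aims with Table 5: two-sided Fisher's exact test, alpha 0.05, and a fall in severe treatment-related adverse events among variant carriers from 60% in historical controls to 30% under genotype guidance. Table 5 gives 80% power at 48 carriers per group. The carrier count comes from a DPYD and/or UGT1A1 frequency of about 10% in the population, so that "testing 500 patients in each group will result in ~50 patients with actionable genotypes". Protocol 5.4 says that "testing 500-800 patients in this multisite study would result in 45-70 patients with the actionable genotypes".

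Protocol 4.1 defines actionable genotypes as "variants that would require a dose adjustment of 5-FU, capecitabine or irinotecan". Table 2 recommends an adjustment for any DPYD activity score below 2 and, for UGT1A1, only for the poor-metabolizer genotypes (*28/*28, *6/*6, *6/*28). Table 1 lists minor allele frequencies by ancestry. Eligibility (5.1) covers patients for whom a fluoropyrimidine and/or irinotecan is indicated.

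SAP item 27 compares severe events between the prospective and historical groups separately among DPYD variant carriers and among UGT1A1 poor metabolizers. SAP item 12 says that no sample size calculation was performed.

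**The concern.** Section 8.1 presents about 10% as the frequency of either genotype in the population. Yet the Table 1 frequencies put UGT1A1 poor metabolizers alone at 10.5% (European ancestry) or 14.2% (African ancestry), before any DPYD carrier is counted. Either the rate is wrong for the group named, or a different group was meant and not described.

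The difference matters because the two genes act through different drugs. A UGT1A1 poor metabolizer who never receives irinotecan has no guided dose change, so the assumed fall from 60% to 30% cannot apply to that patient. The SAP then tests the genes one at a time. If about 50 is read as the size of those comparisons, the 80% row of Table 5 will be credited to analyses that have fewer carriers, and a null result will be given more weight than it can bear.

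**Working it through.** **1. The plan's own figures.** 500 x 10% = 50, as stated. In 5.4, 45/500 = 9.0% and 70/800 = 8.75%. Exact enumeration of the two-sided Fisher test reproduces Table 5: for 60% versus 30%, n = 48 gives 80.05% and n = 54 gives 83.9%. The power table is sound; the question is the carrier rate fed into it.

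**2. Inputs.** From Table 1 (European, African):
- DPYD: *2A 0.008, 0.003; *8 0.0001, not reported; *13 0.001, 0.000; HapB3 0.024, 0.003 (counted once); c.557A>G 0.0001, 0.012; c.2846A>T 0.004, 0.003. Frequencies not reported are taken as 0.
- UGT1A1: *6 0.008, 0.004; *28 0.316, 0.373.

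Ancestry mix from 5.4: "Approximately 20% of the GI cancer population at Penn Medicine is of African ancestry". The other 80% is treated as European, which is an assumption. Hardy-Weinberg proportions and independence of the two genes are also assumed.

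**3. Frequencies by genotype.**

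| Quantity | Formula | European | African | 80/20 mix |
|---|---|---|---|---|
| DPYD carrier | 1 - (1 - q)^2, q = 0.0372 or 0.021 | 7.3% | 4.2% | 6.7% |
| UGT1A1 poor metabolizer | 0.324^2 or 0.377^2 | 10.5% | 14.2% | 11.2% |
| Either | 1 - (1 - D)(1 - U) | 17.0% | 17.8% | 17.2% |

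The union is 85.9 of 500, 103.1 of 600 and 137.5 of 800. UGT1A1-only patients are 17.18% - 6.67% = 10.51%, and 10.51/17.18 = 61% of all actionable patients.

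**4. Sensitivity.** The union stays between 17.0% and 17.8% for any European/African mix. Counting only *28/*28 gives 16.7%. Replacing the Table 1 DPYD frequencies with the 3-5% partial DPD deficiency in 2.2 gives 1 - 0.97 x 0.8876 = 13.9% to 1 - 0.95 x 0.8876 = 15.7%.

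**5. What recovers the stated figures.** Count UGT1A1 only in irinotecan recipients, with share f: rate = 6.67% + f x 10.51%.

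| f | Rate | Per 500 | Per 800 |
|---|---|---|---|
| 20% | 8.8% | 43.9 | 70.2 |
| 30% | 9.8% | 49.1 | 78.6 |
| 50% | 11.9% | 59.6 | 95.4 |

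Exactly 9% needs f = 22% and exactly 10% needs f = 32%. The documents give no value of f.

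**6. Power at the counts the SAP compares.** Two-sided Fisher's exact test, 60% versus 30%, equal numbers of historical carriers. DPYD counts treat every tested patient as a fluoropyrimidine recipient.

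| Group | Tested | Carriers | Power |
|---|---|---|---|
| Planned, pooled | 500 | 50 | 82.9% |
| DPYD carriers | 500 | 33 | 64.6% |
| DPYD carriers | 600 (Table 4 accrual) | 40 | 72.5% |
| DPYD carriers | 800 | 53 | 83.6% |
| UGT1A1 poor metabolizers given irinotecan, f = 30% (assumed) | 500 | 17 | 31% |
| Either gene, all by genotype | 500 | 86 | 97.5% |

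The UGT1A1 count is 500 x 11.24% x 0.30 = 16.9. SAP item 27 names the chi-square test; Fisher's test is used here so that the results compare directly with Table 5.

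**The case against.** The best defence is that 8.1 contrasts carriers on full dose with carriers on guided dose, which makes sense only for a drug the patient receives. On that reading, an irinotecan share of 20% gives 44-70 carriers per 500-800 and 30% gives 49 per 500, close to both stated figures. This stands as a plausible origin for the numbers. It does not remove the gap, because 8.1 cites population frequencies for either gene and neither the restriction nor the share is written anywhere.

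Two further points stand in part. Table 1 reports allele frequencies, so a reader should not infer that it states 17%; that figure is derived. Section 5.2 also excludes bilirubin above 1.5 x ULN, and 10.2.1 links *28/*28 and *6/*6 to Gilbert syndrome, so some UGT1A1 poor metabolizers may be screened out. The documents do not let this loss be sized.

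A reader might infer that the study is underpowered as a whole. The documents do not support that: counted by genotype, the pooled group is larger than planned, and on the drug-received reading about 50 stands. Only the separate gene comparisons fall short, and Table 5 itself already shows 63.6% at 36 per group. Nor should much be made of 10% of 500-800 being 50-80 rather than 45-70, since both figures are approximate.

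Finally, effectiveness is a secondary aim, and the SAP dates the analyses to May-June 2024, so restating planning counts changes no analysis. That limits the consequence to how the results are read.

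**Conclusion.** The concern holds in a limited form. The rate of about 10% does not follow from the protocol's own frequencies for the group that 8.1 names: those imply about 17%, or about 14-16% with the DPD deficiency range in 2.2. It can be recovered through an irinotecan share that is not stated, so this is better described as a missing planning assumption than as a proven arithmetic error.

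The practical effect is on the gene-specific comparisons. At 500 tested, the DPYD comparison has about 65% power rather than the 83% that 50 carriers would give. It passes 80% only towards the upper end of the enrolment range. The UGT1A1 comparison among irinotecan recipients has about 31% at an assumed 30% share.

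These values rest on Hardy-Weinberg proportions, independent genes, the 80/20 ancestry split, unreported frequencies taken as zero, no loss from the bilirubin exclusion, equal numbers of historical carriers, and the 60% and 30% rates applying to each gene separately.

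**What to change.** - In 5.4 and 8.1, define the planning group as patients actionable for a drug they receive, and state the assumed irinotecan share with a range.
- Replace the 10% rate and the 45-70 count with counts derived from Table 1: DPYD carriers among fluoropyrimidine recipients, UGT1A1 poor metabolizers among irinotecan recipients, and their union.
- Give the power at the per-gene counts that SAP item 27 compares, with the expected number of historical carriers for each gene.
- Reconcile 8.1 with SAP item 12, for example by saying that the implementation aims had no calculation while Table 5 was prepared for the effectiveness aims.

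The cost is a revision of text and one table. No extra patients are needed. The drawback is that the stated power for the gene-specific comparisons becomes less favourable.
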